6.7 Final Assessment

At the 48 week timepoint, or when the subject withdraws from study, we will ask them to fill out the previously well-validated System Usability Scale (SUS) questionnaire on a tablet rating their experience with the Carevive software and care plans.

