2.3. Secondary Aim

2.3.1. Collect preliminary data on RCC patients' symptoms, health care utilization, quality of life, distress level and oral drug adherence while on targeted therapy or immunotherapy.

- To determine how patients' treatment-related toxicities correlate to their quality of life, distress level, drug adherence and health care utilization.

3.0.CHARACTERISTICS OF THE RESEARCH POPULATION

3.1 Number of Subjects: We expect to recruit 50 advanced renal cell carcinoma patients from the genitourinary oncology program at Wilmot Cancer Institute of the University of Rochester Medical Center over a one-year period.

3.2 Gender of Subjects: Both men and women will be enrolled in this study. Advanced RCC is known to be almost twice as prevalent in men than women [24], therefore we can expect a roughly 2:1 male to female enrollment rate.

3.3 Age of Subjects: We will recruit patients 18 years and older for this study, however RCC is very uncommon in patients <45 years of age and typically affects adults between the ages of 45 and 84 [1].

3.4 Racial and Ethnic Origin: This study has no enrollment restrictions based upon race or ethnic origin. RCC is known to be less prevalent in Asian and Pacific Islanders [1].

3.5 Inclusion Criteria:

- 3.5.1 Diagnosis of histologically confirmed renal cell carcinoma of any subtype with either pathological or radiographic evidence of metastatic disease
- 3.5.2 Greater than 18 years of age
- 3.5.3 A participating Wilmot Cancer Center oncologist has determined that candidate should be started on either oral targeted therapy or immunotherapy for treatment of their advanced RCC; this can be for first-line or any subsequent line therapy**
- 3.5.4 Able to provide written informed consent
- 3.5.5 Proficient in the English language and self-reports as literate
- 3.5.6 Must have an active email address or access to a smart device

3.6 Exclusion Criteria:

- 3.6.1 Women cannot be breast-feeding
- 3.6.2 Does not have regular access to the internet
- 3.6.3 Unable to come to the Wilmot Cancer Center for appointments every 3-4 months for routine visits with their primary oncologist
- 3.6.4 Subjects who were on the study previously will not be allowed to re-enroll in the event of a treatment change

3.7 Vulnerable Subjects: No special classes of subjects such as fetuses, neonates, children, pregnant women, prisoners, institutionalized individuals or other vulnerable populations will be recruited.

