6.0. METHODS AND STUDY PROCEDURES

6.1 Overview of Study:

We will conduct a phase II, single-arm clinical trial to assess the feasibility of reporting and managing side effects from oral targeted therapy or immunotherapy, through Carevive software, in patients who have advanced RCC. The study will begin when the consented subject starts a new therapy, either an oral targeted agent (pazopanib, sunitinib, axitinib, cabozantinib, lenvatinib, everolimus) or infusional immunotherapy (nivolumab), and will continue for a duration of 48 weeks or until drug is permanently discontinued by their primary oncologist. All study subjects will be asked to log their symptoms through Carevive software weekly for 12 weeks and then every other week for the next 36 weeks. Based on their symptoms, subjects will receive self-management instructions through the software (if applicable). Subjects will also be asked to monitor their medication compliance and health care utilization through the Carevive software once every four weeks for the length of the study. In addition, subjects will be asked to fill out a survey at their medical oncology office visits approximately every 3 months. This survey will include a distress assessment and a quality of life questionnaire. During these visits, a clinician will formally assess the subject's medication related adverse events. At the end of the study, the subject will be asked to fill out an in-office survey rating the usability of the Carevive software. On study completion, the subject's electronic medical record will be reviewed to determine health care utilization and oral targeted therapy refill history during the study period.

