6.6 In-Office Assessments (Week 12, 24, 36 and 48)

Every 3-4 months at routine visits, the physician will perform a toxicity check and will document the grade of the following CTCAE parameters in the subject’s electronic medical record: diarrhea, nausea, vomiting, fatigue, abdominal pain, rash, anorexia, weight loss, oral mucositis, cough and shortness of breath. The subject will again be asked to fill out a FKS-DRS quality of life survey and the “NCCN Distress Thermometer and Problem List for Patients” on a tablet or computer while they are in the office.

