12.3.3 Quality of Life

Subjects will be asked to fill out the Functional Assessment of Cancer Therapy-Kidney Symptom Index (FKSI-DRS) at baseline and approximately every 3 months in-office on a tablet device, with the help of the study team if needed. The FKSI-DRS is a 15-item index of the most important symptoms and concerns of people with advanced kidney cancer which has been determined to be reliable and valid when used in this setting [27].

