12.3.4 Distress Level

The subject will be asked to rate their distress level in-office using the NCCN Distress Thermometer and Problem List for Patients [28], which is a 1 to 10 numerical scale. This will be delivered during routine office visits approximately every 3 months on a tablet.

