12.3.6 Health Care Utilization

The subject's health care utilization will also be assessed by two measures. First, every four weeks via the Carevive survey, the subject will be asked about hospitalizations, emergency or urgent care visits, and unanticipated office visits to their primary care provider in the past month. At the end of the study or at time of withdrawal, a search of the electronic medical record will be performed to determine the number of calls made to oncology care providers and the number of visits to the oncologist.

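### Quality of life, distress and clinician-graded toxicity are not scheduled when a subject stops treatment early, although the usability scale is collected at that contact

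*Combined protocol and SAP*

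**What the plan says.** All references are to the combined protocol and SAP.

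- **End of participation.** Section 6.1 says the study "will continue for a duration of 48 weeks or until drug is permanently discontinued by their primary oncologist".
- **Exit contact.** Section 6.7: "At the 48 week timepoint, or when the subject withdraws from study, we will ask them to fill out the" SUS, on a tablet. Section 6.1 describes this as an in-office survey.
- **Quality of life, distress and clinician toxicity.** The section heading fixes the weeks: "6.6 In-Office Assessments (Week 12, 24, 36 and 48". Its text begins "Every 3-4 months at routine visits, the physician will perform a toxicity check". Section 12.3.3 places the FKSI-DRS "at baseline and approximately every 3 months in-office on a tablet device", and 12.3.4 says of the Distress Thermometer: "This will be delivered during routine office visits approximately every 3 months on a tablet". None of these sections, nor 12.3.2, names discontinuation as a trigger.
- **Records at exit.** Section 12.3.6: "At the end of the study or at time of withdrawal, a search of the electronic medical record will be performed". Section 12.3.5 does the same for refill history, and 7.2 requires the reason for early withdrawal on a CRF.
- **Schedule table, Treatment D/C column.** Marked: software utilisation, care-plan utilisation, SUS, chart-based utilisation and pharmacy-confirmed adherence. Blank: FKSI-DRS, Distress Thermometer, CTCAE, PRO-CTCAE and the patient-reported adherence and utilisation items.
- **Analysis.** Section 15.2 correlates patient-reported toxicity with quality of life, distress, adherence, utilisation and physician-reported toxicity by Spearman's coefficient. It states no analysis time point and no rule for missing values.

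**The concern.** Treatment change and adverse events are both listed in 7.2 as grounds for withdrawal. Subjects who leave early are therefore likely to include those with the worst toxicity, and toxicity is one side of every correlation in 15.2. For these subjects the plan normally has a recent symptom survey, because PRO-CTCAE runs weekly and then every other week until exit (6.5). It has no scheduled quality-of-life score, distress score or physician grade from the same period to set against that survey.

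The consequence is that pairs from periods of high toxicity would be under-represented in three of the five planned correlations. Criterion 3.6.4 bars re-enrolment after a treatment change, so the values cannot be picked up later. The Treatment D/C column shows that the authors planned for this event and already expect a tablet questionnaire at it.

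**Working it through.** **The plan's own figures.** The plan gives no number on this point. Its two precision figures, an interval width of 0.254 at 75% compliance and 0.57 SD for the mean SUS, both reproduce with n = 50 (exact binomial, and 2 × t(0.975, 49)/√50 = 0.568). Neither depends on the measures at issue.

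**Step 1. What exists near exit, from the schedule.**

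| Measure | Last value before exit | Collected at exit |
|---|---|---|
| PRO-CTCAE | normally within 1–2 weeks | no |
| Adherence, utilisation | four-weekly survey | yes, refill history and chart |
| Software and care-plan use | continuous log | yes |
| SUS | none earlier | yes |
| FKSI-DRS, distress, clinician CTCAE | week 0, 12, 24 or 36 | no |

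Only the last row lacks both a recent value and an exit value. A subject who stops before week 12 has week 0 alone. One who stops just before the next visit has a value about 24 − 12 = 12 weeks old, or about 4 × 52/12 ≈ 17 weeks if visits are 4 months apart.

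**Step 2. How many subjects.** Input from 3.1: "We expect to recruit 50 advanced renal cell carcinoma patients". Time to permanent discontinuation is not given. Assumption: exponential with median m weeks, so the share stopped by week w is 1 − 2^(−w/m).

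| m (weeks) | Stopped before week 12 | of 50 | Stopped before week 48 | of 50 |
|---|---|---|---|---|
| 24 | 0.293 | 14.6 | 0.750 | 37.5 |
| 36 | 0.206 | 10.3 | 0.603 | 30.2 |
| 48 | 0.159 | 8.0 | 0.500 | 25.0 |
| 72 | 0.109 | 5.5 | 0.370 | 18.5 |
| 96 | 0.083 | 4.1 | 0.293 | 14.6 |

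So about 4 to 15 of 50 would have baseline values only on the three measures.

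**Step 3. Effect on a correlation.** Assumptions, none from the documents: toxicity and outcome are bivariate normal with r = −0.5, and 25% of subjects are missing under a logistic model in toxicity. The true Spearman coefficient is (6/π) × arcsin(−0.25) = −0.48. Large simulations give:

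| Odds of being missing, per SD of toxicity | Spearman in those observed | Mean toxicity in those observed |
|---|---|---|
| × 2.7 (e¹) | −0.46 | −0.22 SD |
| × 7.4 (e²) | −0.42 | −0.32 SD |

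For scale, the Fisher-z 95% interval around −0.48 at n = 50 is tanh(−0.523 ± 1.96/√47) = −0.67 to −0.23. A shift of 0.02 to 0.06 lies well inside it.

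**Step 4. Effect on precision.** If the baseline-only subjects contribute nothing, the interval on the Fisher-z scale widens by √(47/43) = 1.05 with 4 lost and √(47/32) = 1.21 with 15 lost.

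**The case against.** The case against giving this much weight has several parts, and most of them stand.

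- **A reader might infer that only the SUS and chart or pharmacy data are kept at exit.** The table also marks software and care-plan logs, and 7.2 puts the withdrawal reason on a CRF, so toxicity-related exits can be identified. None of this supplies the three missing measures.
- **A reader might infer that all secondary outcomes are lost at exit.** They are not. Adherence and utilisation are asked every four weeks and also taken from refill history and the chart. PRO-CTCAE continues until exit. The gap is confined to the FKSI-DRS, distress and clinician CTCAE.
- **A reader might infer that the correlations describe only those who tolerated treatment.** That goes too far. On the assumed durations, 71% to 92% reach week 12 and can give at least one post-baseline pair, including many who stop later. Early leavers have a full baseline set (6.4), and 15.2 does not restrict the analysis to post-baseline values. Steps 3 and 4 treat some subjects as wholly absent, so they show a harsh case.
- **The size is assumed and small.** Neither the durations nor the odds ratios come from the documents, and the resulting shift is within sampling error.
- **The aim is preliminary.** Section 2.3 sets out to collect preliminary data, and no test or threshold rests on these coefficients. The primary outcome is untouched.
- **A CTCAE grade needs a clinician.** It is not a tablet item, so the cost is a little more than questionnaire time.

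What survives is the gap itself. Text and table agree on it, and nothing elsewhere in the plan fills it, although a stop may happen to coincide with a routine visit.

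**Conclusion.** The point holds for three measures: FKSI-DRS, Distress Thermometer and clinician CTCAE. They have no scheduled assessment at discontinuation. Subjects who stop before week 12 have baseline values only, and later leavers have a last value up to about 12 weeks old, or longer with visits 4 months apart. Because 7.2 foresees withdrawal for adverse events or treatment change, the loss is probably, though not demonstrably, related to toxicity.

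The number affected is unknown. It is about 4 to 15 of 50 with baseline values only, if duration is exponential with a median of 24 to 96 weeks. The distortion of a Spearman coefficient is probably modest, from −0.48 to between −0.46 and −0.42 under strong assumed dependence. The documents do not support reading this as a threat to the feasibility conclusion. It is an inexpensive improvement to the secondary aim.

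**What to change.** 1. In 6.7 and the Treatment D/C column, add the FKSI-DRS and the Distress Thermometer, completed on the tablet at the contact where the SUS is already given.
2. At the same contact, record the CTCAE grades listed in 6.6 when the subject is seen by the oncologist.
3. Omit both if an in-office assessment took place in the previous two weeks.
4. In 15.2, state that exit values enter the correlations, each paired with the nearest PRO-CTCAE survey. Section 15.2 defines no analysis time point, so calling the exit value a subject's last assessment would not be enough.

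The cost is a short amendment, a few minutes of respondent time (the FKSI-DRS has 15 items) and a brief clinician grading. Some leavers will not attend, so the gap will shrink but not close.

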7.0. SUBJECT CONSENT AND WITHDRAWAL

7.1 Informed Consent

Current state, federal and institutional regulations concerning informed consent will be followed. Participation in this study is voluntary. Subjects are free not to take part or to withdraw at any time, for whatever reason, without risking loss of present or future care they would otherwise expect to receive. In the event that a subject does withdraw from the study, the information they have already provided will be kept in a confidential manner. Subjects may discontinue participation in the study at any time if they decide they do not wish to take part any longer.

7.2 Withdrawal

Subjects may be withdrawn from the study by research personnel if it is deemed in their best interest to no longer participate (for example, in the event that treatment needs to be changed).

The investigators may withdraw the subject from the study in the event of concurrent severe illness, adverse events, other reasons concerning the health or well-being of the subject, or in the case of lack of cooperation, non-compliance, or other administrative reasons.

Reasons for withdrawal of the subject prior to completion of the study must be stated in a Case Report Form (CRF) and in the site source documentation for all study subjects who were enrolled.

8.0. DATA AND SAFETY MONITORING

This study is considered to be of minimal risk and low complexity and will follow the Data Safety Monitoring Plan outlined below:

1. Study investigators will conduct continuous review of patient accrual, eligibility, data collection, and patient safety;
2. There are no or minimal side effects expected related to the study intervention(s);
3. The Data Safety Monitoring Committee will monitor the study on an annual basis through review of RSRB reports;
4. This study may be selected for audit as part of the DSMC data monitoring activities.
5. In the event of an unexpected AND possibly related toxicity the Study Investigator is responsible for notifying the Safety Office of DSMC Chair within 10 calendar days.

9.0. RISK/BENEFIT ASSESSMENT

9.1. Benefits to Subjects

It is expected that participation in this study will involve minimal risk to the participant. Potential benefits from participation include improved symptom assessment and management of drug-induced side effects. Knowledge gained from this study may help improve these activities for cancer patients in the future. As such, it is expected that the benefits of this study outweigh the potential risks. There are no monetary or other secondary benefits.

9.2 Risks to Subjects

This survey study is expected to pose minimal risk to participants. Potential risks include a breach of confidentiality and respondent burden, particularly for cancer patient participants. It is expected that a patient's level of burden will vary based on their overall condition, family and social support and participation in other research studies. Risks of using electronic devices to answer surveys include use of data if not connected to wireless free internet and loss of confidentiality if devices or computers are shared.

9.3 Adequacy of Protection against Risk

To minimize respondent burden, we will inform all participants that participation in the proposed study is voluntary and they may discontinue participation at any time. This study involves obtaining access to subject's medical records and steps must be taken to protect both participant data and identity. The following confidentiality protection steps will be taken: 1) Research staff will participate in initial training, follow-up training, and ongoing monitoring and supervision to ensure understanding of the ethical issues involved in this research. 2) Only the research staff will know the name, identification number, and contact information of participants. The list that links the participant's name with ID number will be kept on an encrypted drive accessible only by the research staff. 3) Consent forms will be kept in locked filing cabinets on the second floor of the Wilmot Cancer Center, in a restricted area with swipe access and will be accessible only by research

staff, and 4) any personal identifiers linked to data will be removed and replaced by non-identifying ID numbers in all records. The electronic files that contain quantitative data will be stored on secure University of Rochester Medical Center file server. These files will be password protected and accessible only by the WCC study team.

In addition, the Carevive electronic platform complies completely with HIPAA standards. Security and confidentiality of the data is ensured through a variety of steps: 1) secured/encrypted SSL/TLS connections, 2) user accounts with unique usernames and passwords, 3) HIPAA compliant cloud hosting for all data stored within the Carevive platform through Firehost, Inc., a company that specializes in secure cloud hosting (<http://www.firehost.com/secure-cloud/compliant/hipaa>). To mitigate risk associated with using electronic devices, we recommend that all devices are password protected and that the subjects log off of their web browser and/or email application prior to leaving their device unattended. We also advise the avoidance of the employer's computer to access the surveys.

10.0 Costs to the Subject

The subject will not incur any direct costs as a result of participation in the study. As stated above, all subjects will be on standard of care therapies, which will be prescribed by their oncology team. The subject's insurance and/or the subject will be billed for their standard of care treatment just as they would if they were not participating in this study. Scheduled in-office assessments and surveys will be done at routine clinic visits and will not result in any additional charges.

1.0 Payment for Participation

There will be no reimbursements or payments of any kind for participation in this study.

12.0 A COLLECTION AND MEASURES

12.1 Primary Study Outcome Measures: The primary outcome will be the feasibility of implementing at home side effect self-assessment and monitoring software.

12.1.1 Carevive Survey Usage Rates

Carevive software will track subject compliance with survey login and whether they access the generated care plans. The clinical team will be notified if a subject misses a login after failing to respond to a reminder notification.

12.1.2 Reasons Participants Do Not Complete Survey or Utilize Care Plans

At the following login, subject will be asked the reason they did not login in the previous time point/time points (if applicable) and why they did not access the care plan.

12.1.3 Software Usability Scoring:

At the 48 week time point or at the point of subject withdrawal from study, they will be asked to take the System Usability Scale [25]. This is a 10 question survey where responses range from "Strongly Disagree" to "Strongly Agree," which are ranked with corresponding numbers. The survey provides us with a score of between 0 and 40 which is then multiplied by 2.5 to convert to a scale of 0 to 100. A SUS score above a 68 would be considered above average and anything below 68 is below average [25].

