2.2. Primary Aim

2.2.1. Assess the feasibility of Carevive software implementation for at-home monitoring and management of treatment-related toxicities from oral targeted agents/immunotherapy among patients with metastatic RCC.

- To determine the demand for this intervention by examining the number and percentage of subjects with RCC who 1) use Carevive software to report their treatment-related symptoms; and 2) utilize the Carevive software generated care plan for management of their treatment-related toxicities.
- To determine the practicality of the intervention, by analyzing the reasons why subjects fail to self-report treatment-related toxicities or utilize software generated care plans after enrollment.
- To assess the acceptability of this intervention with validated patient reported usability scores of the software.
- To determine potential implementation obstacles of the intervention, by assessing the reasons eligible study candidates decline participation.

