The initial survey will occur in office at the week 0 time point. Carevive will then email the subject a link to the survey weekly for the first 12 weeks and then every other week for 36 weeks, to complete 48 weeks or until the subject comes off of the study. This survey will consist of PRO-CTCAE adverse event questions. Subjects will then be provided with self-care management through this automated system. Self-care plans provide advice on managing the symptoms one is experiencing. For example, if the questionnaire indicates a subject is having “occasional” diarrhea, they will be instructed to try an over the counter anti-diarrheal, loperamide, and to keep a stool diary to identify any triggers. They will also be instructed to call the office if their bowel movements increase to 4 or more per day. If the diarrhea is instead rated as “frequently” or “almost constant” the subject will again be instructed to try loperamide but they will also be told to call their cancer care provider immediately, while also stressing the importance of hydration (drinking 8-10 glasses of water daily), and modifying the diet to avoid caffeine, alcohol, spicy foods and dairy.

Every four weeks the survey will also include questions about healthcare utilization and drug adherence. If a subject misses a login they will be sent a reminder the following week, if they miss two logins Carevive will notify our staff who will follow-up with them via telephone.

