15.0. DATA ANALYSIS AND MONITORING

15.1 Primary Outcomes:

Primary Aim 1: *To evaluate the feasibility and usability of symptom monitoring and management with Carevive software.* Specifically, we will determine the demand for this intervention by calculating the rate of compliance. For example, in the case of monthly compliance, the

proportion of subjects who log in at least once during this time frame will be reported. The threshold criteria for compliance based on previous studies [29-30], will be a monthly compliance of 75% (ie. during each month, an average of at least 75% of the subjects completed at least one Carevive survey). Compliance will be determined for both survey completion and access of generated care plans. A sample size of 50 subjects produces a two-sided 95% confidence interval with a width of 0.254 for a point estimate of 75% compliance. Separately patient-level compliance will be determined, based on the proportion of logins that the subject completed during the course of the study. Reasons for noncompliance will be elicited at their subsequent login and will be reported descriptively.

Patient-rated usability, based on their SUS survey results, will also be employed as a measure of feasibility. This survey will be administered to subjects at the end of the study. A Score of >68 indicates greater than average usability [25]. We will determine overall mean usability scores, and we can produce a 95% confidence interval for the mean with a width of 0.57 standard deviations, utilizing the sample of 50 subjects.

We will also determine potential implementation obstacles for Carevive software by asking patients who fail to consent to the study to provide their reasoning. This will be reported descriptively. We will also keep track of the proportion of patients who are approached who fail to consent.

15.2 Secondary Outcomes:

Primary Aim 2: *To determine how patient-reported toxicities correlate to the subject's quality of life, distress level, drug adherence, health care utilization and physician reported toxicities.* Grading of each symptom and numeric values for quality of life, distress level, drug adherence and health care utilization rate will be determined as described in the "Data Collection and Monitoring Section." The strength of the association between symptom grade and each outcome will be measured using the Spearman's rank correlation coefficient.

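### Reasons for not using the software are to be asked only at the next login, so subjects who fall silent while still on study give none to the practicality analysis

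*Combined protocol and SAP*

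**What the plan says.** Section 2.2.1 states that practicality will be judged "by analyzing the reasons why subjects fail to self-report treatment-related toxicities or utilize software generated care plans after enrollment".

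Two places say how the reasons are obtained, and they agree:

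- Section 12.1.2: "At the following login, subject will be asked the reason they did not login in the previous time point/time points (if applicable"), with the same question covering care plans: "and why they did not access the care plan".
- Section 15.1: "Reasons for noncompliance will be elicited at their subsequent login and will be reported descriptively".

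Other contacts with non-users exist:

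- Section 6.5 provides a reminder after one missed login, and "if they miss two logins Carevive will notify our staff who will follow-up with them via telephone". Section 12.1.1 describes a similar alert: "The clinical team will be notified if a subject misses a login after failing to respond to a reminder notification". Neither says that a reason is asked or recorded.
- Section 7.2: "Reasons for withdrawal of the subject prior to completion of the study must be stated in a Case Report Form (CRF"). Non-compliance is among the grounds on which investigators may withdraw a subject, at their discretion.
- Section 6.6 has in-office assessments at weeks 12, 24, 36 and 48, covering toxicity, quality of life and distress.
- Section 6.7 gives the System Usability Scale (SUS) at week 48 or at withdrawal.

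None of these is named as a source of reasons for non-use in 2.2.1, 12.1.2 or 15.1. The schedule table has a row for consent failure but none for reasons for non-use.

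**The concern.** The reason for not using the software is collected through the software. Whether a reason is observed therefore depends on the behaviour under study: a subject who returns can explain the gap, and one who does not return is never asked. Subjects who give up on home reporting while still taking the drug bear directly on whether 48 weeks of it is practical, and the stated rule leaves them out. Reasons that were not collected cannot be recovered in the analysis. Because 15.1 plans no count of non-users without a reason, a reader of the results could not see how much is missing.

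The plan handles refusals differently. Reasons for declining the study go into a screening log outside the software (4.2, 6.3, 12.1.4). Enrolled non-users have no equivalent.

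**Working it through.** **The plan's own figures.** The plan states no number for reasons. Its two precision figures in 15.1 reproduce and do not depend on this point:

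- Compliance: n = 50, p = 0.75, exact (Clopper-Pearson) limits with x = 37.5. Lower = Beta quantile 0.025 with parameters (37.5, 13.5) = 0.607; upper = Beta quantile 0.975 with parameters (38.5, 12.5) = 0.862. The width is 0.254, as stated.
- SUS mean: width = 2 × t(0.975, 49 df) / √50 = 0.568 SD, stated as 0.57.

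**Who reaches the question.** Setting the sections side by side gives:

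| Subject | Next login? | Reason from the stated route? | Other record |
|---|---|---|---|
| Misses, then returns | yes | yes | none needed |
| Completes survey, leaves care plan unopened | yes, unless it was the last login | yes, with that exception | none stated |
| Misses the last scheduled survey (week 48 if on study throughout) | no | no | none stated |
| Stops logging in, still on study and on drug | no | no | call in 6.5, content not stated |
| Stops and is formally withdrawn | no | no | withdrawal reason on the CRF (7.2) |
| Drug permanently discontinued | participation ends (6.1) | not applicable to later surveys | later surveys are not missed surveys |

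**Size, under assumptions.** The documents give no rate of missing or stopping. Let q be the number of the 50 subjects who miss and later return, and s the number who stop for good while surveys are still due. Assume q from 10 to 20 and s from 5 to 15, and that every returner answers. The share of non-using subjects reached is q / (q + s):

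| | s = 5 | s = 10 | s = 15 |
|---|---|---|---|
| q = 10 | 10/15 = 67% | 10/20 = 50% | 10/25 = 40% |
| q = 15 | 15/20 = 75% | 15/25 = 60% | 15/30 = 50% |
| q = 20 | 20/25 = 80% | 20/30 = 67% | 20/35 = 57% |

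The range is 40% to 80%. The share of permanent stoppers whose final stop is explained by this route is 0/s = 0% in every cell, whatever q and s are. If some returners do not answer, the shares in the table fall.

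**The case against.** The best defence is that the plan has more contact with non-users than the two collection sentences suggest. Every early withdrawal needs a stated reason, and the listed grounds include severe illness, adverse events and non-compliance. Staff telephone after two missed logins; they may well ask why, and the call may bring the subject back to a login where the question appears. The SUS at withdrawal captures some difficulty with the software, and in-office visits show how ill a silent subject is. All of this stands and narrows the gap. It does not close it. Withdrawal for non-compliance is optional, so a silent subject may have no withdrawal form. A withdrawal entry may say no more than non-compliance. The call has no stated reason capture, and none of these contacts is named as a source for the analysis.

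Several stronger readings are tempting, and the documents do not support them:

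- *That anyone who stops leaves no reason at all.* Section 7.2 contradicts this for subjects formally withdrawn, and under 6.1 those whose drug is permanently discontinued are no longer due surveys.
- *That a fixed share of non-use, such as half, goes unexplained.* Any such figure comes from chosen inputs. Counting missed surveys also inflates the gap: one subject silent from week 14 to week 48 misses (48 − 14)/2 + 1 = 18 surveys but is one missing explanation.
- *That the missing reasons decide feasibility.* The benchmarks in 15.1 are 75% monthly compliance and a SUS score above 68. Reasons are descriptive and enter neither.
- *That returners will offer only minor reasons.* Nothing in the documents says what they will report.

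**Conclusion.** The point holds as a selective collection rule for one descriptive component of the primary aim. As written, 12.1.2 and 15.1 obtain reasons only from subjects who log in again. Subjects who go silent while still on study and on drug, and those who miss their last scheduled survey, contribute none to the practicality analysis. For care plans the gap is narrower: it concerns mainly a plan left unopened at a subject's last login.

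The size cannot be known from the documents. The 40% to 80% range rests on the assumed counts and on every returner answering; the zero for permanent stoppers follows from the rule itself. The compliance estimate, the SUS estimate, their thresholds and the sample size are unaffected.

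**What to change.** In 12.1.2 and 15.1, state that a reason for non-use, coded from one list to be defined in the protocol, is recorded not only at the next login but also at:

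- the telephone call already planned in 6.5;
- the in-office visits in 6.6;
- withdrawal or treatment discontinuation, as an item separate from the withdrawal reason required by 7.2.

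Add a row for this item to the schedule table.

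In 15.1, report reasons by subject and give the number of non-users from whom no reason was obtained. Show this separately for subjects who later logged in again and for those who did not log in again before leaving the study. Count only surveys due while the subject was on study.

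The cost is one added question at contacts that already take place, a short code list, and a slightly longer descriptive table. No new visits, no change in sample size and no change to clinical management are needed.
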